#### 5.7.4 Electrocardiograms

Cardiac function testing includes 12-lead ECG, Holter ECG and LVEF assessment

A 12-lead ECG is carried out:

- At screening
- During Cycle 1: on Days 1, 2 (only **Part A**), 3 (only **Part A**), 8, 15 and 22
- During other Cycles on Day 1 and Day 15

- At EOT visit
- At unscheduled visits.

A Holter ECG is done:

- At baseline

Only for **Part A**:

- During Cycle 1: on Days 1 and 8
- During Cycle 2: on Day 1
- At EOT visit

Assessment of LVEF via MUGA or ECHO is done:

- At baseline
- During Cycle 1: on Day 8
- During Cycle 3: on Day 1
- At EOT visit

Details of the ECG analyses will be covered by a separate SAP created by BMS.

Results of LVEF assessments (not done, normal, abnormal not clinically significant and abnormal clinically significant) will be summarized by cohort and time point and listed. If either result is missing for any patient, then an 'Unknown' category will be presented.

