### 2. Exclusionary concurrent medical conditions

- a. Impaired cardiac function or clinically significant cardiac diseases, including any one of the following:
1. Clinically significant cardiac disease including congestive heart failure (NYHA class III or IV), arrhythmia or conduction abnormality requiring medication, or cardiomyopathy
  2. Clinically uncontrolled hypertension (systolic blood pressure  $\geq 160$  mmHg or diastolic blood pressure  $\geq 100$  mmHg)

3. Complete left bundle branch block
  4. Right bundle branch block + left anterior hemiblock
  5. Mandatory use of a cardiac pacemaker
  6. Congenital long QT syndrome
  7. History or presence of sustained or symptomatic ventricular tachyarrhythmia
  8. Presence of atrial fibrillation
  9. Clinically significant resting bradycardia (< 50 bpm)
  10. Corrected QTcF > 450 ms for males and > 470 ms for females at the screening ECG
  11. QRS  $\geq$  110 ms
  12. History of symptomatic congestive heart failure
  13. Left ventricular ejection fraction (LVEF) < 50%. History of absolute decrease in LVEF of  $\geq$  15 absolute percentage points, or  $\geq$  10 absolute percentage points and crossing from > lower limits of normal (LLN) to < LLN on prior anti-cancer therapy (e.g. anti-HER2 therapy, anthracyclines), even if asymptomatic
  14. Angina pectoris  $\leq$  6 months prior to starting study drug
  15. Acute myocardial infarction (MI)  $\leq$  6 months prior to starting study drug
- b. General conditions or other clinically significant diseases, including any one of the following:
1. Haemorrhagic, embolic, or thrombotic stroke within 6 months prior to the first planned CB-103 treatment
  2. For patients with solid tumours: prior bone marrow/haematopoietic stem cell transplant.  
**Note:** For T-ALL patients prior allogenic bone marrow/haematopoietic stem cell transplant is allowed if they have no current GvHD and patients are off immunosuppressive therapy.
  3. Known infection with human immunodeficiency virus (HIV); or hepatitis B or C requiring treatment
  4. Any active infection requiring the use of parenteral anti-microbial agents or that is > Grade 2
  5. Non-malignant interstitial lung disease or pneumonitis
  6. Dyspnoea of any cause requiring supplemental oxygen therapy and dyspnoea at rest due to complications of advanced malignancy and co-morbidities

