### 8.2.3.3 Cardiac Imaging – ECHO or MUGA

An ECHO or MUGA should be performed at baseline (within 7 days of first treatment), at Day 8 Cycle 1, at Day 1 Cycle 3 and at EOT visit to assess LVEF. These assessments will be done locally and may be repeated at the Investigator's discretion if there are signs or symptoms of cardiotoxicity. The ECHO or MUGA scans will be reviewed, signed and dated by the Investigator or designee in a timely fashion and print-outs must be filed with the source documentation. The data records will be sent to the CRO for collection and storage. Details for the ECHO and MUGA scans will be provided in a separate Laboratory Manual.

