**9.2.4 Criteria for Withdrawal from the Study**

Patients will be withdrawn from the study if the following criteria are met:

- Unequivocal disease progression
- Death
- Intervening illness that prevents further administration of treatment
- Unacceptable adverse events
- Intercurrent cardiac disease, especially drop in LVEF < 40% or drop > 15% from baseline (if LVEF with > 15% drop is still > 55% a second measurement after 1 week would be allowed before discontinuing the patient)
- Intercurrent interstitial lung disease or pneumonitis
- Patient non-compliance
- Pregnancy
- The patient decides to withdraw from study or is lost to follow-up
- General or specific changes in the patient's condition that render the patient not eligible for further treatment in the judgment of the Investigator
- If a patient experiences a DLT
- If a patient requires a continuous dose delay of more than 14 days (Part A and Part B) from the intended day of the next scheduled dose of CB-103
- If a patient is non-compliant and misses or forgets more than 3 sequential dosings on more than 1 occasion

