### 2.5 Primary Variable(s)

The primary endpoint for Phase I, Part A (dose-escalation) of this study is as follows:

- The number of patients experiencing dose-limiting toxicity (DLT) during the first 28-day cycle of CB-103 treatment

The primary endpoint for Phase I, Part A (confirmatory) of this study is as follows:

- The incidence rate, severity and relationship to CB-103 of adverse drug reactions and serious drug reactions according to common terminology criteria for adverse events (CTCAE) V4.03, safety laboratory, vital signs, ECG and ECHO/MUGA assessments.

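### The SAP tabulates LVEF only by category, so a fall that meets the protocol's more-than-15%-from-baseline withdrawal limb can be counted as normal, and no summary table shows LVEF change

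*SAP*

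**What the plan says.** SAP section 5.7.4 is the only place that specifies an LVEF analysis: "Results of LVEF assessments (not done, normal, abnormal not clinically significant and abnormal clinically significant) will be summarized by cohort and time point", with a listing as well. A missing result goes into an unknown category. The section defines neither normal nor clinically significant. Protocol section 10.6.1 covers adverse events, laboratory values, vital signs and ECG, and has no LVEF analysis. The separate plan mentioned in SAP 5.7.4 is described as covering the ECG analyses.

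The protocol itself uses LVEF as a number and as a change:

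- **Entry.** The exclusion criteria (Protocol 6.1.2, cardiac conditions) rule out "Left ventricular ejection fraction (LVEF) < 50"%. They also rule out certain past falls in LVEF, which are stated in absolute percentage points.
- **Schedule.** Protocol 8.2.3.3 says "An ECHO or MUGA should be performed at baseline (within 7 days of first treatment"), and again at Cycle 1 Day 8, Cycle 3 Day 1 and end of treatment. Scans are done locally.
- **Withdrawal.** Protocol 9.2.4 lists "Intercurrent cardiac disease, especially drop in LVEF < 40% or drop > 15% from baseline", and adds "if LVEF with > 15% drop is still > 55% a second measurement after 1 week would be allowed before discontinuing the patient".

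SAP section 2.5 names ECHO/MUGA in the primary endpoint of the confirmatory cohort ("safety laboratory, vital signs, ECG and ECHO/MUGA assessments"), and SAP section 5.7 lists LVEF results among the safety endpoints.

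**The concern.** A withdrawal limb defined by change from baseline cannot be seen in a table that records only how each scan was classified at each visit. Entry at 50% or above means patients start at or near the normal range, so a fall can be substantial and still end inside it. The protocol's own clause about a fall that leaves LVEF above 55% describes such a patient, and no planned summary would show that patient's fall.

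The omission also stands out within the SAP. Laboratory values (5.7.2) and vital signs (5.7.3) get change from baseline, and vital signs get notable-change thresholds. LVEF gets neither.

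What is at stake is how well the report can describe cardiac safety at the dose carried forward. Protocol section 3.2 says the scans are there to look for an effect on contractility, and it lists reduced ejection fraction among the events that might appear.

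**Working it through.** The plan states no LVEF figure to reproduce. The check is threshold arithmetic: for which baselines can a patient meet the more-than-15% limb and still have a follow-up value at or above the lower limit of normal?

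**Inputs**
- Withdrawal limbs: LVEF below 40%, or a fall of more than 15% from baseline (Protocol 9.2.4).
- Entry floor: 50% (Protocol 6.1.2).
- Lower limit of normal, LLN: not given in either document. I assume 50% to 55%, the entry floor and the cut-off in the repeat-measurement clause.
- Meaning of the 15%: Protocol 9.2.4 does not say whether it is absolute points or relative percent, so both are shown.

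**Formulas**, with baseline B and follow-up F
- Absolute reading: B − F > 15 and F ≥ LLN together require B > LLN + 15.
- Relative reading: (B − F)/B > 0.15 and F ≥ LLN together require B > LLN/0.85.

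**Results**

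| Assumed LLN | Absolute points: B above | Relative percent: B above |
|---|---|---|
| 50% | 50 + 15 = 65% | 50/0.85 = 58.8% |
| 55% | 55 + 15 = 70% | 55/0.85 = 64.7% |

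**Examples**
- 72% to 56%: the fall is 72 − 56 = 16 points, and 16/72 = 22.2% relative. The limb is met under both readings, LVEF is still above 55%, and the value is at or above any LLN in the assumed range.
- 66% to 56%: the fall is 10 points, and 10/66 = 15.2% relative. The limb is met only under the relative reading, so the unstated unit changes who is counted.

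**The other limb.** A value below 40% is more than 10 points below even the lower assumed LLN (50 − 40 = 10), so it would not be expected in the normal category. The problem is confined to the change-from-baseline limb.

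**The case against.** The strongest reply is that the information is not lost. SAP 5.7.4 also lists LVEF results, and SAP 5.1 says all data are listed. Dose cohorts have 3–6 patients, so a fall could be read off a listing. Protocol 9.1.1 counts a worsening test result that leads to a treatment change or discontinuation as an adverse event. SAP 5.7.1 tabulates events leading to interruption or discontinuation, and SAP 5.2 tabulates reasons for stopping. The Cohort Review Committee reviews available safety data from the confirmatory cohort at least quarterly.

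Much of this stands. A reader might infer that patients withdrawn for an LVEF fall would disappear from the report. The documents do not support that, because acted-on cases have several other routes into it. What no summary shows is the distribution of change and the number of patients meeting the limb, whether or not anyone acted. A listing computes neither. In a confirmatory cohort of about 45, with three scheduled post-baseline scans each, that leaves up to 45 × 3 = 135 readings to compare by hand.

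Other stronger readings also go too far:

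- **That such a fall will be tabulated as normal.** It can be. A local reader may call a 16-point fall abnormal and clinically significant, but nothing in the SAP requires it.
- **That meeting the limb means immediate withdrawal.** When LVEF is still above 55%, Protocol 9.2.4 allows a second measurement first.
- **That numeric LVEF is itself a primary endpoint.** The wording in SAP 2.5 can fairly be read as ECHO/MUGA feeding the incidence of adverse reactions. LVEF is in any case a listed safety endpoint.
- **That a patient's scans may freely switch between ECHO and MUGA.** Protocol 8.2.3.3 leaves scan details to a Laboratory Manual, which may hold a same-method rule.

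**Conclusion.** The concern holds for the change-from-baseline limb. As written, the SAP can tabulate as normal a fall that meets a protocol withdrawal limb, and it has no summary of LVEF change. With an assumed LLN of 50–55%, the affected patients are those with baselines above 65–70% (absolute points) or above 58.8–64.7% (relative). The documents do not show how many patients that is, because they give no baseline LVEF distribution.

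This is a reporting gap in a named safety endpoint and is worth closing. It does not show that cardiac withdrawals would be concealed or that the conclusion on the recommended dose is unsound. The result rests on the assumed LLN, on a local reader classifying the follow-up value by its level, and on the separate ECG plan not covering LVEF, which is how that plan is described.

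**What to change.** In SAP 5.7.4, add:

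- LVEF (%) and change from baseline, summarised by cohort and visit;
- worst post-baseline change per patient, summarised by cohort;
- the number of patients with LVEF below 40%, and the number with a fall of more than 15, counted both as absolute points and as relative percent;
- a flag on any change calculated between an ECHO and a MUGA reading.

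Keep the category table as secondary. Show both counts until Protocol 9.2.4, which gives no unit for the 15%, has been reconciled with the exclusion criterion, which specifies absolute percentage points. Which reading applies is for the sponsor to settle, and the SAP addition need not wait for it.

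The cost is one SAP paragraph and one table, with no new assessments. This assumes that the numeric LVEF is on the eCRF or in the scan records that Protocol 8.2.3.3 sends to the CRO. That should be confirmed first: the entry and withdrawal rules oblige the site to know the value, but Protocol 8.2.3.3 describes the transfer to the CRO only as collection and storage.

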### **5.7.5 Physical Examination and ECOG status**

A physical examination by body system (i.e. general appearance, eyes, ears and nose, skin, head, respiratory including throat, cardiovascular, renal and urinary, gastrointestinal, musculoskeletal, nervous system and other) is performed at following time points:

- At screening
- At baseline
- During Cycle 1: on Days 2 (only **Part A**), 3 (only **Part A**), 8, 15 and 22
- During other Cycles on Day 1 and Day 15
- At EOT visit
- At unscheduled visits.

Abnormal, clinically significant findings will be summarized by cohort and time point. All physical examination results will be listed.

ECOG performance status is assessed at screening, at baseline, during cycle 1 on days 2, 3, 8, 15 and 22, during all other cycles on days 1 and 15 as well as at EOT, at safety FU and at unscheduled visits. It will be summarized by dose group and time point and listed.

## **5.8 Pharmacokinetic Assessments**

### **5.8.1 Pharmacokinetic Analysis**

Samples for PK profiles is done at following timepoints:

In Part A:

- During Cycle 1:
  - on Day 1: pre-dose, 0.5h, 1h, 2h, 4h, 6h, 8h, 12h post-dose
  - on Day 2: 24h post Day 1 dose, pre-dose
  - on Day 3: pre-dose
  - on Day 8: pre-dose, 0.5h, 1h, 2h, 4h, 6h, 8h
  - on Day 9: 24h post Day 1 dose, pre-dose
  - on Day 15: pre-dose, 1h post-dose
  - on Day 22: pre-dose, 1h post-dose

In case an oral BID dosing regimen of CB-103 is implemented, the PK sampling scheme during cycle 1 will be adjusted as follows:

- on Day 1: pre-dose, 1st intake, 0.5h, 1h, 2h, 4h post-dose
- on Day 1: pre-dose, 2nd intake, 0.5h, 1h, 2h, 4h post-dose
- on Day 2: pre-dose, 1st intake
- on Day 8: pre-dose, 1st intake, 0.5h, 1h, 2h, 4h post-dose
- on Day 8: pre-dose, 2nd intake, 0.5h, 1h, 2h, 4h post-dose
- on Day 9: pre-dose, 1st intake
- on Day 15: pre-dose, 1st intake
- During Cycle 2:
  - on Day 1: pre-dose, 0.5h, 1h, 2h, 4h, 6h and 8h post-dose
  - on Day 15: pre-dose
- All further Cycles:
  - Each visit: one sample, any time

The following PK parameters will be calculated using non-compartmental methods as data permit for each dose:

- Maximum observed plasma concentration ( $C_{max}$ )
- Minimum observed plasma concentration ( $C_{min}$ )
- Time to maximum plasma concentration ( $t_{max}$ )
- Time to last measurable plasma concentration ( $t_{last}$ )
- Concentration at last measurable plasma concentration ( $C_{last}$ )
- Area under the plasma concentration-time curve up to 8h ( $AUC_{(0-8)}$ )
- Area under the plasma concentration-time curve up to 24h ( $AUC_{(0-24)}$ )

- Total area under the plasma concentration-time curve from time zero to infinity ( $AUC_{(0-\text{inf})}$ )
- Accumulation ratio (AR)
- Terminal-phase elimination rate constant ( $\lambda_z$ )
- Elimination half-life ( $t_{1/2}$ )
- Apparent clearance of drug after oral administration (CL/F)
- Apparent volume of distribution ( $V_d/F$ )
- Apparent volume of distribution at steady state ( $V_{ss}/F$ )

Non-compartmental analysis will be performed using Phoenix WinNonlin version 6.3.

For each PK parameter, individual and mean data, i.e. summary statistics (including number of patients, arithmetic mean together with SD, geometric mean and CV% [except for  $t_{\text{max}}$  and  $t_{\text{last}}$ ], median, Min and Max) will be presented.

Area under the plasma concentration-time curve to the last observable plasma concentration [ $AUC_{(0-t)}$ ] will be calculated from the observed data using the linear up logarithmic down trapezoidal method. Total area under the plasma concentration-time curve from time zero to infinity [ $AUC_{(0-\text{inf})}$ ] will be then estimated by  $AUC_{(0-\text{inf})} = AUC_{(0-t)} + C_t/\lambda_z$ , where  $C_t$  will be the observed concentration at the last quantifiable time point.

The accumulation ratio (AR) is defined as  $AR = AUC_{(0-24)} \text{ Day 8} / AUC_{(0-24)} \text{ Day 1}$ .

The terminal-phase elimination rate constant ( $\lambda_z$ ) will be estimated by log-linear regression of those data points visually assessed to be in the terminal phase of the profile. At least three terminal plasma concentrations after  $C_{\text{max}}$  will be used for estimating  $\lambda_z$ . Elimination, i.e. terminal-phase, half-life ( $t_{1/2}$ ) will be calculated as  $t_{1/2} = \ln 2/\lambda_z$ , apparent clearance of drug after oral administration as  $CL/F = \text{Dose}/AUC_{(0-\text{inf})}$ , apparent volume of distribution as  $V_d/F = \text{Dose}/(\lambda_z \cdot AUC_{(0-\text{inf})})$  and volume of distribution at steady state  $V_d/SS = \text{Dose} \cdot AUMC_{(0-\text{inf})}/AUC_{(0-\text{inf})}^2$ , where AUMC is the area under the first moment curve.

Individual CB-103 plasma concentration-time data will be listed and graphically displayed for each patient both on linear as well as on semi-logarithmic (on concentration axis) scale for Cycle 1 Day 1, Cycle 1 Day 8 and Cycle 2 Day 1, where C1D1, C1D8 and C2D1 profiles will be overlaid for all individuals by cohort and day.

Summaries of plasma concentrations will be presented in tabular form by assessment time-point (Cycle, day within cycle and time post study drug intake). Also for Cycle 1 Day 1, Cycle 1 Day 8 and Cycle 2 Day 1, the mean (+/-SD) plasma concentrations will be displayed graphically over time on linear as well as on semi-logarithmic (on concentration axis) scale for each cohort and for each visit across cohorts. A graph of the pre-dose mean (+/-SD) concentrations for all days where a PK plasma sample is drawn will be provided, with both individual curves by cohort and average curves across cohorts.

Plots of key PK parameters ( $C_{\text{max}}$ ,  $AUC_{(0-\text{inf})}$ ) vs dose including all visits in one plot figure will be provided.

All PK summaries are based on the PK Set and will also be provided by indication i.e, for solid tumours or T-ALL/T-LBL and by ethnicity.

All derived PK parameters will be listed for all patients in PK set and summarized within cohort.

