### 2.5.3.2 Prediction of Human PK from Non-Clinical Studies (Allometric Scaling)

Allometric scaling for CB-103 using mouse, rat and dog intravenous (i.v.) PK data was performed to predict the human PK parameters CL, volume of distribution at steady state ( $V_{ss}$ ) and  $t_{1/2}$ .

Table 2 summarises the prediction along with the input values for the scaling. No correction for plasma protein binding was performed as the differences across species is minimal (binding approx. 98% in all species).

**Table 2** Pharmacokinetic parameters observed in mouse, rat and dog and predicted for humans using allometric scaling

Species	Mouse	Rat	Rat	Dog	Human
Data Source	CB-103-ADME010	CB-103-ADME011	CB-103-T002	CB-103-T001	PREDICTED
Body weight	0.025 kg	0.3 kg	0.38 kg	12 kg	70 kg
CL (mL/h/kg)	3627.5	2481.3	3940	456	
CL (mL/h)	90.7	744.39	1497.2	5472	23520
Vss (mL/kg)	1664.8	1125.3	897	5670	
Vss (L)	0.042	0.338	0.341	68.0	380
T1/2 (h)	0.49	0.73	0.157	10.2	16.2
Bioavailability (F)	100%	16.3%	15.4%	81%	
Plasma Protein Binding (%)	98.3	98.2		98.7	97.0

Data in bold are measured, data in italics are calculated. Parameters for humans are predicted.

For the human predicted values of CL 23520 mL/h (or 23.52 L/h) and of  $V_{ss}$  380 L, the estimated half-life ( $V_{ss}/CL$ ) is around 16 hours. It is therefore expected that CB-103 needs about 3 to 4 days to reach steady state concentrations. With daily administration, the predicted accumulation ratio (AR) would be 1.5. The first dose level administered in this clinical protocol is 15 mg (fixed dose) and the expected AUC at this dose is 639  $\mu\text{g}\cdot\text{h}/\text{mL}$

assuming complete bioavailability of the compound after oral administration. If the bioavailability of CB-103 in humans is less than 100% the exposure will be respectively lower.

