One patient in cohort 8 (600mg) experienced one dose limiting toxicity (DLT). This was an elevation of the gamma-glutamyl transferase (GGT), grade 3, that was asymptomatic and deemed not clinically significant by the investigator. There has been one unrelated SAE with fatal outcome due to respiratory tract infection in cohort 1 (15 mg). No deaths due to drug-related AEs have been reported to date.

CB-103 is rapidly absorbed after oral administration and reaches Cmax within 1 to 2 hours of dosing. Plasma exposure increases with increasing doses. There were no signs of saturated absorption in the dose range tested. The elimination half-life is approximately 20 hours and CB-103 accumulates about 2-fold with repeated daily administration. Steady state concentrations are reached within one week of dosing.

Hair follicles used as surrogate tissue were obtained at pre-defined time points to measure changes in NOTCH target genes expression by CB-103 treatment. In patients in the ongoing phase 1 study, average target gene downregulation on Cycle 2 day 1, 1h post-dose compared to baseline prior to treatment with CB-103 showed a strong dose-dependent down-regulation of several NOTCH target genes, reaching values higher than 70% inhibition at the highest CB-103 dose tested in this series (250mg). Additionally, a sustained time-dependent down-regulation of NOTCH target genes was observed, reaching up to a 90% inhibition after 4 weeks of daily administration of CB-103 at 250mg dose.

Clinically, best response was durable stable disease (SD) with no or only mild AE at doses showing target engagement. Ten patients with ACC had radiologically confirmed SD, of whom 4 patients had a Notch activating mutation or fusion. The Notch status of the other patients is under investigation. Disease control rate (DCR) of 19 ACC patients at 3 months was 68% (DCR defined as number of patients with CR, PR, or SD divided by the number of patients treated).

Based on the safety profile, the Cohort Review Committee declared the dose of 600mg given once daily QD as a safe dose. The MTD was not reached. The Bayesian statistical model allows further dose escalation to 800mg. Because the visual symptoms caused considerable discomfort to some patients, the 600mg dose was declared as provisional RP2D for further exploration in the dose confirmatory cohort. In parallel, a twice daily schedule of CB-103 is being explored.

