**Phase I, Part A - MTD/RP2D confirmatory cohort and Phase IIA, Part B – Expansion:**

**For patients with solid tumours who are not hospitalized:**

- Patients will undergo daily visits for 3 days and will get their CB-103 doses administered in the hospital. Patients will stay for at least 3 hours following each administration of CB-103 to allow safety reporting with the exception of the first day where the patients should stay for up to 8 hours post-dose.

In case CB-103 is given BID, one more overnight hospital stays at Day 8 in cycle 1 may be necessary to allow late samples collection.

- Weekly visits to monitor safety and perform ECG monitoring and PK sampling are planned during the rest of the treatment period for the 1st cycle of CB-103 (28 days).
- Every 2 weeks visits to monitor safety and perform PK sampling are planned from cycle 2 until the completion of cycle 6.
- After cycle 6, subsequent visits are planned every 4 weeks if no medical issue or complication occurred in the previous cycles.
- End-of-Treatment (EOT) visit within 14 days after the last dose of CB-103 (within the 12 cycles period).
- Safety follow-up visit (End-of-Study) for each patient within 28 days after the last dose of CB-103.
- Survival follow-up (e.g. per telephone) for 1 year is planned every three months after the End-of-Study or after the last treatment cycle (if outside of the 12 cycles period), and every six months thereafter for the 2nd year.
- Further visits might be considered, depending on the health status of the patient, as determined by the treating Investigator of the respective investigational site.
- More frequent laboratory safety tests (e.g., to closely monitor the liver function), are possible and can be performed outside the study site for those patients living far away, if necessary. The laboratory reference ranges from the local laboratories must be collected and filed in the laboratory report together with the patients' medical records. Care should be taken that any outliers possibly produced by the local laboratory findings are investigated at the study site.

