**Part A pharmacokinetic sample collection (for patients on a once-daily dose regimen of CB-103) will be obtained on:**

### **Cycle 1 (total of 22 samples):**

- Day 1: pre-dose, 0.5, 1, 2, 4, 6, 8 hours post-dose ( $\pm$  5 minutes) and 12 hours post-dose ( $\pm$  15 minutes)
- Day 2: 24 hours post Day 1 dose ( $\pm$  60 minutes), before drug intake on Day 2
- Day 3: pre-dose
- Day 8: pre-dose, 0.5, 1, 2, 4, 6 and 8 hours post-dose ( $\pm$  5 minutes)
- Day 9: 24 hours post Day 8 dose ( $\pm$  60 minutes), before drug intake on Day 9
- Day 15: pre-dose and 1 hour post-dose ( $\pm$  5 minutes)
- Day 22: pre-dose and 1 hour post-dose ( $\pm$  5 minutes)

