**Part B pharmacokinetic sample collection will be obtained on:**

**Cycle 1 (total of 22 samples):**

- Day 1: pre-dose, 0.5, 1, 2, 4, 6, 8 hours post-dose ( $\pm$  5 minutes) and 12 hours post-dose ( $\pm$  15 minutes)
- Day 2: 24 hours post Day 1 dose ( $\pm$  60 minutes), before drug intake on Day 2
- Day 3: pre-dose
- Day 8: pre-dose, 0.5, 1, 2, 4, 6 and 8 hours post-dose ( $\pm$  5 minutes)
- Day 9: 24 hours post Day 8 dose ( $\pm$  60 minutes), before drug intake on Day 9
- Day 15: pre-dose and 1 hour post-dose ( $\pm$  5 minutes)
- Day 22: pre-dose and 1 hour post-dose ( $\pm$  5 minutes)

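### AUC(0-inf), the exposure measure plotted against dose, is about 44% extrapolated on 24 h profiles and about 76% on the 8 h C2D1 profile, and the SAP sets no span or extrapolation limit

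*SAP*

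**What the plan says.** Protocol 2.5.6 gives the observed kinetics: "The elimination half-life is approximately 20 hours and CB-103 accumulates about 2-fold with repeated daily administration".

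SAP 5.8.1 samples C1D1 "on Day 1: pre-dose, 0.5h, 1h, 2h, 4h, 6h, 8h, 12h post-dose". A 24 h sample follows, which Protocol 8.4 places "before drug intake on Day 2". C1D8 is sampled to 8 h and again at 24 h. Cycle 2 is sampled "on Day 1: pre-dose, 0.5h, 1h, 2h, 4h, 6h and 8h post-dose", with nothing later that day or the next morning outside the PK sub-studies.

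For the terminal slope, SAP 5.8.1 says that it "will be estimated by log-linear regression of those data points visually assessed to be in the terminal phase of the profile", using no fewer than three terminal concentrations after Cmax. AUC(0-inf) adds the last concentration divided by that slope. CL/F is Dose/AUC(0-inf); Vd/F and Vss/F also use AUC(0-inf), and Vss/F uses AUMC(0-inf) as well. Parameters are calculated where the data allow, but no criterion for that is given. The key parameters plotted against dose are Cmax and AUC(0-inf), with all visits on one figure.

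**The concern.** A half-life of 20 h means that a 24 h profile sees 1.2 half-lives and an 8 h profile 0.4. The part of AUC(0-inf) beyond the last sample is then large, and the slope that supplies it is fitted over a short span. The SAP has a minimum number of points but no minimum span, fit criterion or maximum extrapolated share, so a C2D1 value built on 4, 6 and 8 h satisfies the rule.

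These parameters are secondary endpoints (Protocol 4.2.2, SAP 2.6). The dose plot would mix C1D1 values, C1D8 values that include carry-over from earlier doses, and C2D1 values that are mostly modelled. A reader could not tell a feature of the drug from a feature of the extrapolation. The single CL/F formula adds a bias of its own after repeated dosing.

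**Working it through.** **Inputs.** Half-life 20 h and about 2-fold accumulation (Protocol 2.5.6); predicted half-life 16.2 h (Protocol 2.5.3.2, Table 2), where "With daily administration, the predicted accumulation ratio (AR) would be 1.5"; last samples at 24 h and 8 h (SAP 5.8.1). The residual CV is not in the documents and is assumed, with a range shown.

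**The plan's own figures first.** With once-daily dosing AR = 1/(1 − 2^(−24/t½)). At 16.2 h this gives 1.56 against the stated 1.5. At 20 h it gives 1.77, which agrees with about 2-fold only to the nearest whole number. An AR of exactly 2 needs t½ = 24 h. I therefore use 16.2–24 h as the range.

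**Extrapolated share.** For one compartment with last sample T and k = ln 2/t½: AUC share = e^(−kT); AUMC share = e^(−kT)(1 + kT). At 20 h, k = 0.03466, so kT = 0.832 at 24 h and 0.277 at 8 h.

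| t½ | AUC, 24 h | AUC, 8 h | AUMC, 24 h | AUMC, 8 h |
|---|---|---|---|---|
| 16.2 h | 36% | 71% | 73% | 95% |
| 20 h | 44% | 76% | 80% | 97% |
| 24 h | 50% | 79% | 85% | 98% |

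First-order absorption (assumed rate 1.5–3 per h) moves the 20 h, 24 h figure only to 44–45%. If an assumed early phase carried 10–30% of the AUC, it would be 39–30%. Under linear kinetics the single-dose share beyond 24 h is 1 − 1/AR whatever the number of compartments, so an AR of 2 implies 50%.

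**Span of the slope fit at 20 h.** 2–24 h is 22/20 = 1.1 half-lives; 8–24 h is 0.8; 2–8 h is 0.3; 4–8 h is 0.2.

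**Precision of half-life.** In a log-linear fit, SE(k) = σ/√Sxx with σ² = ln(1 + CV²) and Sxx the sum of squared deviations of the sampling times. For 2, 4, 6, 8 h, Sxx = 20; at 10% CV, σ = 0.0998 and SE = 0.0223 against k = 0.0347. The 5–95% limits below are taken among positive slopes, true t½ 20 h.

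| Points | CV 5% | CV 10% | Slopes ≤ 0 at 10% |
|---|---|---|---|
| C2D1: 2, 4, 6, 8 h | 13–42 h | 10–100 h | 6% |
| C2D1: 4, 6, 8 h | 11–77 h | 7–124 h | 16% |
| C1D1: 4, 6, 8, 12, 24 h | 17–24 h | 15–28 h | 0% |
| C1D8: 6, 8, 24 h | 17–24 h | 15–30 h | 0% |

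**CL/F after repeated dosing.** At steady state, AUC from the dose to infinity is the single-dose AUC(0-inf) multiplied by AR. Dose/AUC(0-inf) therefore returns 1/AR of the true CL/F: 1/1.77 = 56% at 20 h (64% at 16.2 h, 50% at 24 h).

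**The case against.** A reader might infer that half-life, AUC(0-inf), Vd/F and Vss/F are all mostly extrapolation at every visit. The documents do not support that. On the 24 h profiles more than half of AUC(0-inf) is usually observed. Half-life is fitted, so its weakness is imprecision, and on C1D1 it is usable at a 5–10% CV. A majority share holds only for AUC(0-inf) at C2D1 and for the AUMC behind Vss/F.

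A reader might also infer that a dose-proportionality finding or the exposure-response work depends on these values. No dose-proportionality analysis is specified and PK is descriptive (Protocol 10.6.3). AUC(0-8), AUC(0-24) and Cmax are reported anyway, the accumulation ratio uses AUC(0-24), and exposure-response uses population-PK exposure and observed Cmax (Protocol 10.6.4).

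The SAP does ask for terminal-phase points and calculates only where data allow; a non-positive slope would yield no half-life. The half-life ranges depend on an assumed CV. Sub-study patients have a C2D2 pre-dose sample about 24 h after the C2D1 dose (Protocol Appendices 11 and 12), so not every C2D1 profile stops at 8 h.

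All of that stands and limits the point. It does not supply a reliability rule: a point count is not a span, the data-permitting condition has no threshold, and AUC(0-24) is not the measure plotted against dose.

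**Conclusion.** The point holds in limited form and should be acted on. Followed as written, SAP 5.8.1 plots against dose a C2D1 AUC(0-inf) that is about three-quarters extrapolated (71–79%) from a slope spanning 0.2–0.3 half-lives, beside 24 h values that are about 44% extrapolated (36–50%). Vss/F is unreliable at every visit, with 80% of AUMC extrapolated at 24 h and 97% at 8 h. CL/F computed by the stated formula at C1D8 or C2D1 would be about 56% of its true value (50–64%).

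The shares assume one compartment, linear kinetics and once-daily dosing. The precision figures also assume the residual CV. The 20 h half-life presumably came from this same sampling and is itself uncertain. These are secondary, descriptive endpoints: the fault lies in what is reported and plotted, and dose escalation does not turn on it.

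A separate protocol inconsistency should not be read as part of this fault. Protocol 8.1, for confirmatory-cohort and Part B outpatients, has a stay of at least 3 hours after each dose "with the exception of the first day where the patients should stay for up to 8 hours post-dose", while Protocol 8.4 schedules a Day 1 sample at 8 h "and 12 hours post-dose" and Appendix 1 marks an overnight stay on C1D1 unless reduced sampling is implemented.

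**What to change.** In SAP 5.8.1:

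1. Plot Cmax and AUC(0-24) against dose for C1D1 and C1D8, and Cmax and AUC(0-8) for C2D1, in place of AUC(0-inf) for all visits.
2. Derive no parameter that uses the terminal slope from a profile ending at 8 h. Allow C2D1 only where the C2D2 pre-dose sample exists.
3. Restrict AUC(0-inf), Vd/F and Vss/F to C1D1. Report the extrapolated share and the span in half-lives with each value. List values beyond a prespecified limit but leave them out of summaries.
4. Use Dose/AUC(0-24) for CL/F at C1D8. Add half-life and volume to the outputs of the population PK model in Protocol 10.6.4, which at present promises only AUC or CL/F and is not mentioned in SAP 5.8.

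In the same edit, correct the Day 9 sample, which the SAP ties to the Day 1 dose and Protocol 8.4 to the Day 8 dose. Separately, reconcile the Day 1 stay in Protocol 8.1 with the 12 h sample and Appendix 1; that is a protocol change.

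Items 1 to 4 need no new samples. The cost is few or no non-compartmental summaries of AUC(0-inf), Vd/F and Vss/F, and fewer of half-life. The limit must be set knowing this: a 20% ceiling, for illustration, would need sampling to 20 × log2(5) = 46 h (38 h at a half-life of 16.2 h), which daily dosing rules out, so typical C1D1 profiles at about 44% would fail it.
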